7.7 EXTENT OF EXPOSURE

The variables defined in Section 5.4.2 will be summarised descriptively for each dose cohort (phase Ib parts) or treatment group (Phase II part).

7.8 SAFETY ANALYSES

All safety analyses will be performed on the TS (unless otherwise specified; for example, the MTD Set will be used for some safety outputs). Patients in the first part of the trial who were replaced within or before the first treatment cycle will be excluded from the determination of the MTD.

7.8.1 Adverse events

The analyses of AEs will be descriptive in nature. All analyses will be based on the number of patients with AEs (not the number of AEs).

For analysis multiple AE occurrence data on the CRF will be collapsed into an AE event provided that all of the following applies:

- All AE attributes are identical (LLT, CTCAE grade, action taken with trial medication, therapy required, seriousness, reason for seriousness, relationship, outcome, AESI)
- The occurrences were time-overlapping or time-adjacent (time-adjacency of 2 occurrences is given if the second occurrence started on the same day or on the day after the end of the first occurrence)

For further details on summarisation of AE data, please refer to (2) and (4).

AEs will be coded with the most recent version of MedDRA. The severity of AEs will be scaled according to CTCAE (CTCAE version 4.03 (R10-4848)).

The analyses of adverse events will be based on the concept of treatment-emergent adverse events. That means that all adverse events with an onset between first treatment administration until end of the REP will be assigned as 'on treatment'. All adverse events occurring before first drug intake will be assigned to 'screening' and all adverse events occurring after the residual effect period will be assigned to 'post-treatment'; these AEs will be displayed in separate tables and listings. Adverse events will be displayed by the initial dose of study medication administered on the first day of treatment .

An overall summary of adverse events will be presented. The frequency of patients with adverse events will be summarised by treatment, primary SOC and PT. Separate tables will be provided for patients with drug-related AEs, AEs leading to dose reduction, adverse events leading to discontinuation, SAEs, serious drug-related AEs, AEs leading to death, other significant AEs, AESI, and AEs fulfilling the DLT definition (for phase Ib escalation only).

Sorting order:

In tables presenting SOCs and PTs, SOCs will be sorted alphabetically and PTs (within SOC) by descending frequency.

Reporting of CTCAE grades in tables:

In tables showing AEs by worst CTCAE grade, AEs with missing CTCAE grade will only be displayed under the category "All grades", but no category "Missing grade" will be displayed. Therefore the categories "Grade 1" to "Grade 5" might not add up to the category "All grades"; a footnote will explain this handling.

Displaying of CTCAE grades in AE tables (Section 15) will be "All grades", "Grade 1", "Grade 2", "Grade 3", "Grade 4", and "Grade 5" separately. In the appendix (Section 16.1.9.2), the categorisation "All grades", "Grade 1/2", "Grade 3/4/5", will be used.

Listings of AEs

Adverse events will be reported with start and end day as calculated from the first day of treatment with study medication.

Incidence and severity of AEs

The incidence of AEs overall (irrespective of relatedness to study medication), related AEs, and SAEs will be reported by severity according to CTCAE grades.

Other significant AEs

Other significant AEs are defined as serious and non-serious AEs that lead to dose reduction or permanent discontinuation of study medication. Their incidence will be reported by severity according to CTCAE grades.

A listing of patients who developed 'other significant' AEs will be provided and a flag for serious and non-serious will be included.

AEs leading to dose reduction or permanent discontinuation will include:

- AEs leading to dose reduction of xentuzumab
- AEs leading to dose reduction of enzalutamide
- AEs leading to permanent discontinuation of xentuzumab
- AEs leading to permanent discontinuation of enzalutamide

AEs leading to death

AEs leading to death during the on-treatment period will be tabulated in a separate table. In this table no CTCAE grades will be shown. For fatal AEs without CTCAE grade 5 or missing grade, the grade will be imputed as CTCAE grade 5. Reported fatal AEs that occurred in the post-treatment period will be listed within the listing containing all post-treatment AEs.

Protocol-specified AESI

AESIs are specified in the CTP Section 5.2.2.1. Their incidence will also be reported. DLTs are considered as AESIs only in the phase Ib escalation.

Adverse events by user defined AE categories (UDAEC)

UDAEC as defined on project level by the pharmacovigilance working group will be derived and the latest version will be used for the analysis. The categories will be taken as defined in the most recent signed version of the safety statistical analysis plan at the time of DBL. These

categories can also be found in Table 7.8.1:1. This document is entitled "8-02-sap-safety-core", which can be found in the Project DMS folder, section 8 (project level), within BIRDS.

Table 7.8.1: 1 Adverse events by user defined AE categories

Term	Group [#]		
Uanatia impairmant	SMQ: Drug related hepatic disorders – comprehensive		
Hepatic impairment	search SMQ		
Uvnaralyanamia narrayy	SMQ: Hyperglycaemia/new onset diabetes mellitus		
Hyperglycaemia narrow Narrow			
	BIcMQ:		
Infusion related reaction	PT list of Infusion related reaction		
infusion related reaction	AND		
	SMQ Hypersensitivity Narrow		
Non-infectious pneumonitis	SMQ: Interstitial lung disease Narrow		
Renal insufficiency	SMQ: Acute renal failure Broad		
Weight loss	BIcMQ:		
Weight loss	Weight loss - Broad		
Neutropenia	SMQ: Haematopoietic leukopenia – Narrow		
Stomatitis	BIcMQ:		
Stomatitis PT list			
Asthenia	BIcMQ:		
Asincilla	Asthenic conditions – Narrow		
Anemia	SMQ: Haematopoietic erythropenia		
Thrombocytopenia	SMQ: Haematopoietic thrombocytopenia		

This column indicates whether the Term(s) provided in the first column are MedDRA preferred terms (PT), Standardised MedDRA Queries (SMQ) or BI customised MedDRA Queries (BIcMQ).

The incidence of AE by UDAEC will be analysed.

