An exploratory expansion cohort will be pursued in approximately 25 enrolled patients to ensure 21 evaluable patients at the MTD, and/or recommended phase II dose (RP2D) determined in the escalation part of phase Ib described above. A patient is considered evaluable if data for the assessment of the primary endpoint is available. Patients recruited to this cohort will be on ongoing enzalutamide therapy and be beginning to show a rise in PSA (as described in section 3.3.2 inclusion #19) on this treatment at the time of consent for the expansion cohort of the study. These patients will continue to receive enzalutamide from the first day of treatment on the study combined with BI 836845. Patients in this expansion cohort will continue treatment until disease progression, undue toxicities, or discontinuation for any other reason, see section 3.3.4 for details.

Phase II - Randomised phase II:

In phase II, 80 patients will be randomised in a 1:1 ratio to receive treatment with either BI 836845 plus enzalutamide (Arm A) at the MTD, and/or the recommended phase II dose (RP2D) determined in phase Ib escalation, or enzalutamide alone (Arm B), in an open label, parallel group study design. Patients will continue treatment until disease progression, undue toxicities, or discontinuation for any other reason, see section 3.3.4 for details.

After discontinuation of all trial drugs and completion of the final follow up visit, see section 6.1.3, patients will be followed up further (every 90 days after the last follow up visit) for survival status in an observation period (until approval of protocol version 10 after which no further survival status will be collected).

Doc. No.: c02304008-15 Trial Protocol Version 12 Page 35 of 241

Proprietary confidential information. © 2022 Boehringer Ingelheim International GmbH or one or more of its affiliated companies. All rights reserved.

Phase I and Phase II:

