7.3 PLANNED ANALYSES

During phase Ib (escalation), cohorts of patients treated with BI 836845 in combination with enzalutamide will be evaluated continuously based on the safety profile in order to determine the MTD and /or recommended phase II dose. This MTD, and /or recommended phase II dose will be used in the phase Ib expansion cohort and in phase II.

Efficacy analyses will include all randomised patients in phase II. For phase Ib expansion cohort PFS will be summarised on cohort level. No comparisons between dose cohorts will be performed for phase Ib escalation.

Safety analyses will be summarized separately for patients treated in phase Ib and phase II. The safety profile for the phase II patients will be compared in a descriptive manner between the BI 836845 in combination with enzalutamide arm, and the enzalutamide only arm.

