Due to the inherent difficulties determining radiographic progression in this indication, a central imaging unit is employed to interpret the radiographic images and obtain an independent tumour assessment in addition to the investigator's assessment. However, due to these difficulties, there is potentially a high discordance rate between the independent review and the investigators (fewer independent review events compared to investigator assessed events). From Table 7.6: 2 it can be seen that having a discordance rate of going up to 33% – leaving potentially only 40 independent review events – still gives a probability of between 0.66 and 0.74 (corresponding true underling HR of between 0.65 and 0.70) of observing a HR of less than 0.8 in the evaluation of the independent review as well. If the true underlying HR should be 1.0, then the probability of observing a HR of 0.8 is still sufficiently low with 0.24.

Due to the patients' advanced condition and previous treatment regiments obtained before joining this study, the estimated median PFS time in the enzalutamide arm is around 3 months, and between 4.3-4.6 months in the combination arm of BI 836845 + enzalutamide.

² Calculated based on the approximate normal distribution of the estimated log hazard ratio, i.e. assuming the log hazard ratio is normally distributed with mean log(true hazard ratio), and variance (4 / number of PFS events) (R10-4988).

³ Note that 70 events out of 80 patients can only be seen if the number of permanently censored patients is very low.

Proprietary confidential information. © 2022 Boehringer Ingelheim International GmbH or one or more of its affiliated companies. All rights reserved.

Assuming recruitment rates of 10-13 patients per month for a period of A months, the percentage of observed PFS events relative to sample size is a function of study duration T:

$$\frac{1}{2} \left[\left(1 - \frac{e^{-\lambda_1(T-A)} - e^{-\lambda_1 T}}{A\lambda_1} \right) + \left(1 - \frac{e^{-\lambda_2(T-A)} - e^{-\lambda_2 T}}{A\lambda_2} \right) \right].$$

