where λ_1 =0.151 and λ_2 =0.231 are the parameters of exponential distribution assuming median PFS of 4.6 months for BI 836845 in combination with enzalutamide and 3 months for emzalutamide alone. Based on the formula above, and taking multiple parameter combinations into consideration, the study duration until the required numbers of events are obtained is estimated to be between 17-23 months. Therefore, the primary analysis is targeted when 60 PFS events by investigator's assessment are observed or 23 months after the first patient was randomized in the phase II part.

Table 7.6: 3 Study duration until targeted number of 60 PFS events from 80 randomised patients are observed for different possible underlying scenarios

Median PFS	Median PFS	Rate of	Accrual	Expected trial duration to
Enzalutamide	BI 836845 +	permanently		reach the expected
alone	Enzalutamide	censored	period	number of PFS events
[months]	[months]	patients*	[months]	[months]
3	4.3	20%	9	19.9
3	4.6	20%	9	20.6
3	4.3	15%	9	16.4
3	4.6	15%	9	16.9
3	4.3	20%	12	21.9
3	4.6	20%	12	22.5
3	4.3	15%	12	18.4
3	4.6	15%	12	18.8

^{*} Percentage of patients that leave the study without a PFS event

Proprietary confidential information. © 2022 Boehringer Ingelheim International GmbH or one or more of its affiliated companies. All rights reserved.

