7 PLANNED ANALYSES

The labelling and display format of statistical parameters will follow BI standards (8).

Unless otherwise specified, outputs will be displayed separately for each part of the trial.

Descriptive statistics for continuous variables will generally contain number of patients in that patient set with non-missing values (N), Mean, Standard Deviation (SD), Minimum (Min), 25th percentile (Q1), Median, Q3 (75th percentile), Maximum (Max). In general, means, SDs, medians, Q1 and Q3 will be presented to one more decimal place than the raw data. Minima and maxima will be presented to the same number of decimal places as the raw data.

For time-to-event analysis tables, the set of statistics is: number of patients [N (%)], Number of patients with event [N (%)], Number of patients censored [N (%)], <Time to event> [months] followed by Q1 (25th percentile), Median, Q3 (75th percentile). If not specified otherwise, the duration as well as time to event will be displayed in months.

Tabulations of frequencies for categorical data will include all possible categories and will display the number of observations in a category as well as the percentage (%) relative to the respective treatment group total. Percentages will be rounded to one decimal place. In general a category "missing" will be displayed, if there are missing data for the corresponding variable. Percentages will also generally be based on all patients in the respective patient set whether they have non-missing values or not.

The primary analysis will include all treated (phase I escalation and expansion parts) or randomised patients (phase II part), following the ITT approach (as specified in Section 6.3).

Sort order for general categorical variables: If categories correspond to the collected categories on the eCRF and the table shells do not explicitly specify the ordering, the "default ordering" defined by the eCRF is to be used in such cases. If categories are derived the ordering as specified in the table shell document should be used; in general ordinal data (e.g. categorised continuous data) are to be displayed in ascending order.

The denominator of the main categories is defined by the number of patients in the used patient set. The main categories define the denominators of the subcategories. Subcategories should be indented and "[N (%)]" to be displayed only for the main category.

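### If the combination keeps patients on treatment longer, as the sample-size assumptions imply, the crude phase II AE percentages will show an excess in arm A for continuing-risk events even at equal hazards

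*SAP*

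**What the plan says.** SAP 7.8.1 sets the unit of analysis: "All analyses will be based on the number of patients with AEs (not the number of AEs". It continues: "The frequency of patients with adverse events will be summarised by treatment, primary SOC and PT". SAP 7 gives the denominator for categorical tables as "the percentage (%) relative to the respective treatment group total", so person-time does not enter.

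Under SAP 7.8.1 an event is on treatment if it starts between first administration and the end of the residual effect period, which SAP 6.1 sets at 42 days. How long a patient is treated is not fixed. Protocol 3.1 says of phase II: "Patients will continue treatment until disease progression, undue toxicities, or discontinuation for any other reason". For the sample size, Protocol 7.6 assumes that "the estimated median PFS time in the enzalutamide arm is around 3 months, and between 4.3-4.6 months in the combination arm".

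The arms are to be set against each other. Protocol 7.3 states: "The safety profile for the phase II patients will be compared in a descriptive manner". Exposure is summarised by treatment group in SAP 7.7, without a link to the AE tables. No exposure-adjusted rate, time-to-first-event analysis or common time window for AEs appears in the text that can be read.

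**The concern.** The percentage of patients with at least one event depends on both the hazard of the event and the time over which it can be counted. That time ends 42 days after the last dose, and the last dose is tied to progression. If arm A progresses later, its patients are observed for AEs for longer, and the crude percentage rises for any event whose risk continues. This is about time at risk. It would remain if both arms were seen equally often.

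The stake is the reading of the phase II safety comparison. Protocol 2.1 makes the phase II data the basis for the clinical assumptions of a phase III trial. A display that mixes toxicity with duration would count against the combination in the case where it prolongs PFS, and in the same direction for every AE term with continuing risk.

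**Working it through.** **Inputs.** Median PFS 3 months (arm B) and 4.3 or 4.6 months (arm A), exponential, from Protocol 7.6. Residual effect period 42 days from SAP 6.1; with the SAP 7 conversion this is 42 × 12 / 365.25 = 1.38 months. 40 patients per arm from Protocol 3.3. The documents give no AE hazards, so constant hazards r of 0.03, 0.05, 0.10 and 0.20 per month are assumed, the same in both arms.

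**Reproducing the plan's own figure.** The monthly progression rates are ln 2 / 4.6 = 0.151 and ln 2 / 3 = 0.231, as printed. Table 7.6:3 gives 22.5 months for medians 3 and 4.6, 20% permanently censored and 12 months' accrual. The required event fraction is 60 / (80 × 0.80) = 0.9375. The protocol's formula at T = 22.5, A = 12 gives 0.905 in arm A and 0.970 in arm B, mean 0.9375. The other seven durations in the table reproduce as well, so the exponential model below is the one the plan uses.

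**Length of the AE window.** If treatment time is taken as PFS, mean time on treatment is median / ln 2. Adding 1.38 months:

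- arm B: 4.33 + 1.38 = 5.71 months
- arm A, median 4.3: 6.20 + 1.38 = 7.58 months; ratio 7.58 / 5.71 = 1.33
- arm A, median 4.6: 6.64 + 1.38 = 8.02 months; ratio 8.02 / 5.71 = 1.40

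A simulation that cuts follow-up at the planned analysis date (9 months' accrual with analysis at 20.6 months, or 12 with 22.5) gives mean windows of about 5.5 months in arm B and 7.0-7.2 in arm A, a ratio of about 1.26-1.31.

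**Crude percentages at equal hazard.** With progression rate λ = ln 2 / median,

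P(at least one AE) = 1 − exp(−1.38 r) × λ / (λ + r).

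For r = 0.10 in arm B: 1 − 0.871 × 0.231 / 0.331 = 0.392. In arm A with median 4.6: 1 − 0.871 × 0.151 / 0.251 = 0.476.

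| r per month | Arm B | Arm A (4.3 to 4.6) | Excess, points | Crude risk ratio |
|---|---|---|---|---|
| 0.03 | 15.1% | 19.1-20.0% | 4.0-4.9 | 1.27-1.33 |
| 0.05 | 23.3% | 28.8-29.9% | 5.5-6.6 | 1.24-1.29 |
| 0.10 | 39.2% | 46.2-47.6% | 7.0-8.4 | 1.18-1.21 |
| 0.20 | 59.3% | 66.1-67.4% | 6.8-8.1 | 1.11-1.14 |

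The true hazard ratio is 1 in every row.

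**Where the effect fades.** If PFS is the same in both arms, λ is the same and the excess is zero. An event confined to the first month falls inside the window of every patient in both arms, because the residual period alone exceeds a month, so the two percentages agree. For an event that 90% of arm B patients have, the same model gives 92.4-92.8% in arm A.

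**Against sampling error.** With 40 per arm the standard error of a difference is √(2p(1−p)/40): 8.9 points at p = 0.2 and 11.2 at p = 0.5.

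**The case against.** Several objections carry weight.

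- **Nothing plans treatment duration.** The medians are sample-size assumptions for PFS, and Table 7.6:2 also works through a true hazard ratio of 1.0. A reader might infer that equal toxicity will appear as excess toxicity in arm A whatever happens. The documents do not support that: the excess depends on arm A staying on treatment longer.
- **The ratio of medians is not the ratio of windows.** A reader might carry 4.3/3 to 4.6/3, about 1.4-1.5, straight over to the AE window. Both arms receive the same 42 days, which brings the ratio down to 1.3-1.4, and a data cut-off lowers it further.
- **Treatment time is not PFS.** Treatment also stops for toxicity and other reasons, and Table 7.6:3 allows 15-20% of patients to leave without a PFS event. The 4-8 points are therefore near the upper end.
- **The crude percentage is legitimate.** It describes what happened under each regimen as given. The analysis is descriptive, exposure is tabulated by arm, and the shift is at most about one standard error.
- **Incidence rates can mislead the other way.** For a low-probability event that occurs only early and equally often in both arms, dividing by the mean windows gives 5.71/8.02 = 0.71 to 5.71/7.58 = 0.75, so arm A would look about 25-29% safer with no true difference.
- **Absence is not proven.** SAP 7.8.1 refers to company standards for further AE summaries, and SAP 5.4.2 defines the exposure variables. Neither could be seen.

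These points limit the claim and shape the remedy, but they do not remove the problem. A separate exposure table shows an imbalance without correcting any AE percentage for it. The shift, though within sampling error, is systematic across terms with continuing risk. And the SAP text that can be read commits to no time-based display.

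**Conclusion.** The concern holds conditionally. If arm A is treated longer, as the PFS assumptions imply, its AE window averages about 1.3-1.4 times that of arm B. For events with continuing risk and equal hazards of 0.03-0.20 per month, the crude tables would then show roughly 4-8 points more patients with an event in arm A. This rests on exponential treatment time equal to planned PFS, no dropout or data cut-off, and assumed AE hazards.

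It would go too far to conclude that the crude tables are invalid or that rates should replace them. The supported conclusion is narrower: crude percentages alone cannot separate toxicity from duration, and the visible plan adds nothing that does.

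**What to change.** Keep the crude tables. For phase II, add to SAP 7.8.1 the cumulative incidence of first AE by arm at fixed times from first dose, for example 12 and 24 weeks, with death without the AE as a competing event. Do this for any AE, grade 3 or higher, serious AEs, AESIs and the user-defined categories. Give exposure-adjusted incidence rates (patients with a first event divided by time from first dose to first onset or end of the residual period) as a supplement only. State that the between-arm description will be read from the crude and time-based displays together. If the company standards already provide such a display, a sentence committing to it is enough.

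The cost is SAP wording and a few extra tables from dates already collected. There are two limits to state in the SAP. The rates assume a constant hazard and can understate early toxicity in the longer-treated arm. Censoring at the end of the residual period may be informative when treatment stops for toxicity.

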7.8.2 Laboratory data

7.8.2.1 Laboratory data

The analyses of laboratory data will be descriptive in nature and will be based on BI standards (6). The same on-treatment periods as considered for the analysis of AEs will be applied for laboratory values except for that the baseline laboratory value will be included in the 'on-treatment' period. Patients having at least one post-baseline laboratory value will be displayed in the descriptive analyses.

Descriptive statistics, including change from baseline and frequency of patients with transitions relative to the reference range, will be provided. CTCAE grades for applicable laboratory parameters will be calculated according to CTCAE version 4.03 (R10-4848). The following outputs will be presented:

• Worst CTCAE grade experienced during the on-treatment phase.

• Transitions of CTCAE grade from baseline to worst laboratory value, from worst to last laboratory value during the on-treatment phase, and from baseline to last laboratory value.

Patients with missing CTCAE grade at baseline or no baseline value but post baseline values will be displayed in the category "Missing CTCAE grade at baseline". Laboratory values without CTCAE grading will be compared to their reference ranges and frequency tables will be provided for the number of patients within and outside the reference range at baseline and the last measurement on treatment.

Analysis of potentially clinically significant abnormal laboratory values, and handling of CTCAE grade -1 and -9 laboratory parameters, are described in the SOP for "Display and analysis of laboratory data" (6), RD 9.

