3.3.2 Inclusion criteria

- 1. The patient has histologically, or cytologically, confirmed adenocarcinoma of the prostate.
- 2. Male patient aged \geq 18 years old.
- 3. Patients with radiographic evidence of metastatic prostate cancer (stage M1 or D2). Distant metastases evaluable by radionuclide bone scan, CT scan, or MRI within 28 days before the start of study treatment.
- 4. Patients with a PSA ≥ 5 ng/mL.
- 5. Patients with prior surgical or chemical castration with a serum testosterone of <50 ng/mL. If the method of castration is luteinizing hormone releasing level hormone (LHRH) agonists, the patient must be willing to continue the use of LHRH agonists during protocol treatment.
- 6. Eastern Cooperative Oncology Group performance status (ECOG PS) 0 or 1.
- 7. Cardiac left ventricular function with resting ejection fraction ≥50% as determined by ECHO or MUGA.
- 8. Absolute neutrophil count (ANC) ≥1500/uL.
- 9. Haemoglobin ≥9 g/dL.
- 10. Platelets \geq 100,000/uL.
- 11. Bilirubin \leq 1.5 times the upper limit of normal (ULN).
- 12. Aspartate transaminase (AST) and alanine transaminase (ALT) \leq 2.5 times the ULN (or \leq 5 times the ULN if liver metastases are present).
- 13. Creatinine $\leq 1.5 \text{ x ULN}$.
- 14. International normalized ratio (INR) ≤ 2 and a partial thromboplastin time (PTT) ≤ 5 seconds above the ULN (unless on oral anticoagulant therapy). Patients receiving full-

Proprietary confidential information. © 2022 Boehringer Ingelheim International GmbH or one or more of its affiliated companies. All rights reserved.

dose anticoagulation therapy are eligible provided they meet all other criteria, are on a stable dose of oral anticoagulant or low molecular weight heparin (except warfarin or coumarin-like anticoagulants, which are not permitted).

15. Fasting plasma glucose < 8.9 mmol/L (< 160 mg/dL) and HbA1c < 8.0%.

Inclusion criteria only for patients entering phase Ib dose escalation and phase II:

- 16. Patients who have disease progression during, or after, receiving docetaxel and have had at least 12 weeks of treatment and in the opinion of the investigator are unlikely to derive significant benefit from additional docetaxel-based therapy, or were intolerant to therapy with this agent.
- 17. Patients who have disease progression during, or after, receiving abiraterone treatment in any setting.
- 18. Patients must have progressive disease defined as at least one of the following:

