6.7 BASELINE, TIME WINDOWS, AND CALCULATED VISITS

6.7.1 Baseline

The last measurement observed prior to start of trial medication will be assigned to baseline. Note that for some trial procedures (for example body weight, vital signs, laboratory tests) this may be the value measured on the same day trial medication was started. In these cases it will be assumed that the measurements were taken prior to the intake of any study medication. For tumour assessment, baseline evaluations must be based on Magnetic Resonance Imaging (MRI) or Computed Tomography scans performed no more than 28 days prior to start of trial medication.

Study days and visits will be labelled according to the flow chart of the CTP.

Unless otherwise specified, baseline is defined as the latest time-point before the very first administration of any study medication. If this criterion is not fulfilled then no baseline will be derived, except in the following case: if a patient is entered (phase Ib escalation and expansion parts) or randomised (phase II part), but not treated, the last value we have for the patient is considered baseline.

Laboratory values:

Baseline is defined as the latest time-point before the very first administration of any study medication.

If any of these times are missing and the date of laboratory value is equal to the date of first study drug administration, then the laboratory assessment will be considered as according to protocol, i.e. as prior to first study medication.

ECG

Baseline values will be derived from the triplicate at the time-point closest to but prior to the first administration of study medication.

Quality of Life (QOL) questionnaires

BPI-SF questionnaire is assessed at screening and several time-points thereafter. Baseline assessment is the questionnaire assessment from screening, unless it is missing. In this case, the C1V1 assessment is considered baseline.

FACT-P questionnaire is assessed at several time-points starting at C1V1. Baseline assessment is considered as being the assessment from C1V1.

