7.8.2.2 Laboratory values of special interest

Hepatic enzyme elevations (potential Hy's law cases):

These are defined as those cases where a combination of all of the following events occurred: any on-treatment value of alanine aminotransferase (ALT) and/or aspartate transaminase (AST) > 3 Upper Limit of Normal (ULN) with total bilirubin \ge 2ULN and alkaline phosphatase (ALKP) < 2 ULN. The events can occur in any order, but must occur within 14 days of the previous event, i.e. the second event must occur within 14 days of the first event, and the third event must occur within 14 days of the second event, etc.

Patients with missing laboratory values for liver enzymes will be excluded from these analyses but will be presented separately in a listing. Tabulations of hepatic enzyme elevations and liver laboratory values (see Section 5.2.2.1 of the CTP), including flags of true DILI (Drug-Induced Liver Injury) cases, are created in accordance with the Food and Drug Administration (FDA) DILI guidance (P09-12413).

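### The SAP counts the pre-drug baseline laboratory value as on-treatment, so the worst-grade table can report a grade seen only before study drug

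*SAP*

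**What the plan says.** - **Laboratory window.** SAP 7.8.2.1 uses the same on-treatment periods as for adverse events, "except for that the baseline laboratory value will be included in the" on-treatment period.
- **Window being modified.** Under SAP 7.8.1, "all adverse events with an onset between first treatment administration until end of the REP will be assigned as 'on treatment"; events before first intake go to screening.
- **Baseline.** In SAP 6.7.1, "baseline is defined as the latest time-point before the very first administration of any study medication", and the laboratory paragraph there repeats the definition.
- **Outputs.** SAP 7.8.2.1 lists "Worst CTCAE grade experienced during the on-treatment phase" and "Transitions of CTCAE grade from baseline to worst laboratory value". It also lists worst-to-last and baseline-to-last transitions, change from baseline, and reference-range comparisons. Patients are displayed if they have at least one post-baseline value. Further display rules are left to a sponsor SOP that is not among the documents.
- **Liver search.** SAP 7.8.2.2 looks for "any on-treatment value of alanine aminotransferase (ALT) and/or aspartate transaminase (AST") above 3 × ULN, with total bilirubin at least 2 × ULN and alkaline phosphatase below 2 × ULN. The events may come in any order, each within 14 days of the one before.
- **Entry limits.** Protocol 3.3.2 caps bilirubin at 1.5 × ULN (criterion 11). It caps AST and ALT at 2.5 × ULN, or "5 times the ULN if liver metastases are present" (criterion 12).

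**The concern.** A table of worst on-treatment grades is read as what happened after drug was started. If the baseline value is in the pool from which the worst is taken, the worst grade can never be lower than the baseline grade. A patient who enters with a grade 2 abnormality and is better at every later visit then appears as having grade 2 on treatment, and the stand-alone table gives no means of telling.

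The rule also sits badly with the rest of the plan. The same pre-drug abnormality would be a screening finding in the adverse-event tables and an on-treatment finding in the laboratory tables. Protocol 5.2.2.2 treats abnormalities that exist before inclusion as baseline conditions. Entry criteria admit patients with mildly abnormal liver, renal and haematology values, so abnormal baselines can occur. At stake is the clarity of the descriptive laboratory comparison between arms and, to a small degree, of the Hy's law search.

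**Working it through.** The documents state no figure on this point, so there is nothing to reproduce. The check is whether each planned output changes when baseline is in the window.

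**Set-up.** Let *b* be the baseline grade and *p1*, *p2* two post-baseline grades, with *p2* the last. Each runs from 0 to 4, giving 5 × 5 × 5 = 125 patterns.

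- SAP wording: worst = max(*b*, *p1*, *p2*)
- Post-baseline only: worst = max(*p1*, *p2*)

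The patterns are unweighted. The counts show what is possible, not how often it would happen.

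| Output | Condition | SAP wording | Post-baseline only |
|---|---|---|---|
| Worst grade comes only from baseline | *b* > max(*p1*, *p2*) | 30 | 0 |
| Baseline-to-worst, improved | worst < *b* | 0 | 30 |
| Baseline-to-worst, worsened | worst > *b* | 70 | 70 |
| Worst-to-last, improved | *p2* < worst | 70 | 50 |
| Baseline-to-last, improved | *p2* < *b* | 50 | 50 |

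**Arithmetic.**

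- *b* > max(*p1*, *p2*): the sum of *b*² is 0 + 1 + 4 + 9 + 16 = 30.
- Worsened: 125 − sum of (*b* + 1)² = 125 − (1 + 4 + 9 + 16 + 25) = 125 − 55 = 70. The two rules agree because max(*b*, *p1*, *p2*) exceeds *b* exactly when a post-baseline grade does.
- Worst-to-last, SAP wording: 125 − sum of (*p2* + 1)² = 125 − 55 = 70. Post-baseline only: *p2* < *p1* in 10 of 25 pairs, times 5 baselines = 50.
- The excess of 70 − 50 = 20 is the set with *p1* ≤ *p2* < *b*: the sum of *b*(*b* + 1)/2 is 0 + 1 + 3 + 6 + 10 = 20. All 20 lie within the 30 patterns where baseline is worse than every later value.
- Baseline-to-last does not use the worst value: 10 × 5 = 50 under both rules.

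**Example.** Baseline grade 2, then 1 and 1. SAP wording: worst on-treatment grade 2, baseline-to-worst 2 to 2, worst-to-last 2 to 1. Post-baseline only: worst 1, baseline-to-worst 2 to 1, worst-to-last 1 to 1.

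**Hy's law.** An eligible patient can have a baseline transaminase between 3 and 5 × ULN only with liver metastases (criterion 12). Baseline bilirubin is at most 1.5 × ULN, below the 2 × ULN the search needs (criterion 11), and Protocol 6.2.2 has the criteria re-checked before dosing on cycle 1 day 1. So of the two elevations required, only the transaminase one can come from baseline. A bilirubin rise after entry, inside the 14-day limit, is still needed.

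**The case against.** The case for leaving the SAP alone has four parts.

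- **The worsening result is untouched.** This stands: the number of patients who worsen from baseline, and the grade they reach, are the same under both rules. The baseline-to-worst table also shows the baseline grade beside the worst, so a pre-existing abnormality is visible there. The stand-alone worst-grade table has no such column.
- **Few patients may be affected.** In the phase II flow chart used until protocol version 10, safety laboratory tests are weekly in both arms through cycle 3. The best-case reading of baseline's influence is that one value must be worse than all of many later ones. This is fair, and it limits the effect without removing it. Requiring a post-baseline value drops baseline-only patients, not these.
- **The sponsor SOP may use baseline only as a reference.** It may. The documents do not say so, however. The SAP sentence is explicit, and nothing supplied excludes baseline from the search for the worst value.
- **The analysis is descriptive, and toxicity is also captured as adverse events** with a window that starts at first administration. This stands and sets the weight of the point.

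A reader might infer that no improvement can ever appear in the laboratory tables. The documents do not support that: baseline-to-last, worst-to-last, change from baseline and reference-range outputs can all show it. A reader might also infer that chance baseline imbalance between arms passes straight into the toxicity comparison because of this rule. Mostly it does not. An abnormality that persists on drug would be counted after the correction too, so ordinary imbalance would largely remain.

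**Conclusion.** The point holds, with a narrow reach. As written, three outputs are affected, all in patients whose baseline grade is worse than every later grade:

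- the worst-grade table can report a pre-drug grade as on-treatment;
- the baseline-to-worst table cannot show improvement;
- the worst-to-last table can show recovery from a grade that was never reached on drug.

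The Hy's law search is exposed only through its transaminase condition; baseline values alone cannot make an eligible patient a case.

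The size of the effect cannot be estimated, because the documents give neither the frequency of abnormal baselines nor how often they improve at every later visit. The conclusion assumes that the SAP sentence is applied literally and that the unseen SOP does not override it. In the phase Ib expansion cohort patients are already taking enzalutamide, and SAP 6.1 starts their on-treatment period at first xentuzumab, so there the baseline value precedes xentuzumab rather than all drug. No test, estimate or decision rule depends on these tables. This is a minor correction.

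**What to change.** In SAP 7.8.2.1, replace the exception with a statement that the baseline laboratory value serves only as the reference value. Then state that the worst CTCAE grade, the worst-to-last transitions and the potential Hy's law search in SAP 7.8.2.2 use values taken after first study drug up to the end of the residual effect period (42 days, SAP 6.1). Baseline stays as the starting point of the baseline-to-worst and baseline-to-last tables. If the sponsor SOP already excludes baseline from the worst value, a sentence saying so is enough. The cost is one SAP sentence and one date condition in the laboratory program; no data collection changes.
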